## 8. STATISTICAL CONSIDERATIONS

### 8.1. Statistical Design, Method and Analysis Procedure

This study is a prospective, multicenter, randomized controlled study to evaluate the superiority of INTERCEED™ compared to blank control in reducing the incidence of postoperative incision adhesions in laparoscopic surgery.

The primary effectiveness endpoint is the proportion of subjects free of abdominal incision adhesions at primary target incision site observed in the two treatment groups (INTERCEED™ and Control). The assessment of adhesions will be conducted during the second laparoscopy for ileostomy reversal.

The statistical hypotheses for the primary endpoint are as follows:

- $H_0: P_I \leq P_C$  tested against the alternative hypothesis
- $H_a: P_I > P_C$

where  $P_I$  is the proportion of subjects free of adhesions in the INTERCEED™ group and  $P_C$  is the proportion of subjects with adhesions in the Control group.

The proportion of subjects free of adhesions will be summarized for each treatment group and will be calculated as the number of subjects free of adhesions divided by the total number of subjects randomized to that treatment. Within-treatment group two-sided 95% confidence intervals for the proportions of subjects free of adhesions will be provided using Clopper-Pearson method. In addition, a one-sided Wald 97.5% confidence interval for the difference in two independent proportions (INTERCEED™ minus Control) will be constructed and used for testing the null hypothesis of superiority stated above. If the lower limit of the confidence interval is greater than 0, then it will be concluded that INTERCEED™ is superior to Control.

The primary endpoint will be analyzed using the Intent-to-Treat (ITT) and Per-Protocol (PP) sets. The ITT analysis will be considered primary, while the PP analysis will be considered supportive. The analysis sets for this study are defined in section 8.9.

The following secondary effectiveness endpoints will be summarized descriptively by treatment group for the ITT analysis set:

- Extent and severity of adhesions--at the incision site and four abdominal quadrants;
- Incidence of subjects with mechanical ileus.

In addition, the following safety endpoints will be summarized descriptively by treatment group for the Safety analysis set:

- Incidence of subjects with surgical site infections (SSI) of target incision after Phase 1 operation;

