## 8.6. Criteria and Reason for Terminating the Trial based on the Statistical Results

An ad-hoc interim analysis is proposed based on feedback received from the investigators who observed very low rate of adhesions at the second procedure for ostomy reversal.

The conditional power (CP) is the probability that the final result will be significant, given the data obtained up to the time of interim look. The table as below shows the CP per different adhesion rate difference of INTERCEED vs Control arms at the interim look.

Given the assumed 30% drop-out rate, it was planned that a total of 154 participants (77 per arm) with evaluable primary endpoint are available by the study completion. The interim analysis will be performed while at least 94 participants (at least 61% of the total number) have their primary endpoints evaluated in the electronic data collection system. If the CP is  $\leq 60\%$ , the observed adhesion rate difference magnitude between two arms is only around 0.10, which is much less than the assumed difference magnitude of 0.25 used for sample size calculation. Therefore, the study will be terminated due to low adhesion rate and small effect size between INTERCEED and control arms. Otherwise, the study will continue until the study completion as planned.

There is a database lock for this interim analysis. All data for the analysis will be cleaned with 100% source data validation. The statistical analysis will be conducted per updated and approved protocol and SAP to determine if the interim results meet the pre-specified threshold of early discontinuation ( $CP \leq 60\%$ ).

Table: Conditional power per different treatment effect size observed at interim look

Observed adhesion difference between INTERCEED vs control at interim look	Data availability at interim look				
	Percentage of participants with evaluable primary endpoint (number of participants)				
	61% (94)	66% (102)	70% (108)	72% (112)	75% (116)
-0.02	0.19	0.11	0.07	0.04	0.02
-0.06	0.35	0.26	0.2	0.16	0.12
-0.08	0.45	0.37	0.3	0.26	0.21
-0.1	0.55	0.48	0.42	0.38	0.34
-0.11	0.59	0.54	0.49	0.45	0.41
-0.12	0.64	0.6	0.56	0.52	0.49
-0.13	0.69	0.65	0.62	0.6	0.57
-0.14	0.73	0.7	0.68	0.66	0.64
-0.15	0.77	0.75	0.74	0.72	0.71

-0.16	0.81	0.8	0.79	0.78	0.78
-0.18	0.87	0.87	0.87	0.87	0.87

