## **8.7. Statistical Method of All Data, together with the Handling Method of Missing, Unused and Error Data (including Termination and Withdrawal Halfway) and Unreasonable Data**

All study endpoints will be analyzed using the available data. There will be no missing data imputation in this study.

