2.1 General Rules

Statistical analysis will be performed using SAS 9.4 or higher version statistical software. The two-sided 95% confidence interval for the proportion of subjects free of adhesions in the treatment groups will be provided by the Clopper-Pearson method. In addition, the two-sided Wald 95% confidence interval for the difference of two independent proportions (experimental group minus control group) will be constructed and used to test the null hypothesis for the superiority. If the lower limit of the confidence interval is greater than 0, it can be concluded that the experimental group is superior to the control group. Descriptive statistics will be adopted for statistical analysis, and the continuous variables will be summarized using the number of cases, mean, standard deviation, median, quartiles, maximum, and minimum; the categorical variables will be summarized using the missing value, number of cases, and percent. Unless otherwise specified, the number of subjects without missing data in the analysis set selected will be used as the denominator for percent calculation. [Table 2](#) describes the numbers of decimal places kept for the statistical parameters.

Table 2 Number of Decimal Places Reserved for the Statistical Parameters

Statistics	Number of Decimal Places Reserved
Mean, median	Keep one more decimal place than the source data, but not more than 3 decimal places
Standard deviation, 95% confidence interval	Keep two more decimal places than the source data, but not more than 3 decimal places
Maximum, minimum	Keep the same decimal place as the source data, but not more than 3 decimal places
Percent	Keep one decimal place, express the percent as “100” if it reaches a hundred percent, and express it as “0” if it is 0

P value	Keep three decimal places, and express it as P < 0.001 when all the first three decimal places are 0
---------	--

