2.3.5 Handling of Missing Data

For the primary endpoint (presence or absence of adhesions), no imputation will be made for missing data during primary analyses. However, during the sensitivity analysis, the missing primary endpoint will be imputed by the Multiple Imputation (MI) method. When developing MI model, the following baseline variables and the variables for phase 1 operation will be used, including the subject's age, gender, randomized adhesion barrier product used during phase 1

operation, presence or absence of adhesions during phase 1 operation, duration of phase 1 operation, blood loss and incision length, and radiotherapy or chemotherapy used at baseline or not.

The secondary endpoint will be analyzed based on the ITT set. No imputation will be made for missing data. All secondary study endpoints will be analyzed using available data.

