3.3 Effectiveness Endpoints Analysis

3.3.1 Primary Effectiveness Endpoint Analysis

The primary effectiveness endpoint is the proportion of subjects free of incision adhesions at the main target incision site observed in the two groups (experimental group and control group). The ITT and PP analysis sets will be used to analyze the primary effectiveness endpoint. The ITT analysis will be regarded as the primary analysis, and PP analysis as supportive analysis.

The statistical hypotheses for the primary endpoint are as follows:

- $H_0: P_I \leq P_C$
- $H_a: P_I > P_C$

Where P_I is the proportion of subjects free of adhesions in the experimental group, and P_C is the proportion of subjects free of adhesions in the control group.

The proportion of subjects free of adhesions in each treatment group will be summarized and calculated as: number of subjects free of adhesions divided by the total number of subjects randomized to receive the treatment. The two-sided 95% confidence interval for the proportion of subjects free of adhesions in the treatment groups will be provided by the Clopper-Pearson method. In addition, the two-sided Wald 95% confidence interval for the difference of two independent proportions (experimental group minus control group) will be constructed and used to test the null hypothesis for the superiority. If the lower limit of the confidence interval is greater than 0, it can be concluded that the experimental group is superior to the control group.

```
proc freq data =data;
  weight count;
  tables group*outcome / riskdiff(CL=WALD);
run;
```

Furthermore, a sensitivity analysis for the primary endpoint will be added. The stratification factor “presence or absence of neoadjuvant radiotherapy” will be adjusted to estimate the rate difference of the two groups and corresponding 95% CI.

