3.5 Analysis of Other Endpoints

3.5.1 Study Product Defects

The study product defects will be tabulated.

4 Interim Analysis and Data Monitoring Committee (DMC)

Based on the feedback from the investigator that the target incision adhesion rate observed during the phase 2 operation (ileostomy reversal) is very low, an interim analysis will be added. The interim analysis will be performed after at least 94 subjects (accounting for at least 61% of the total subjects) have completed the primary endpoint evaluation.

The timeline for the interim analysis is September 15, 2020.

The interim analysis will include the following subjects:

- a) All subjects that have undergone the phase 2 operation,
- b) Subjects who withdrew from the study without undergoing the phase 2 operation;
- c) Subjects who have neither undergone the phase 2 operation nor withdrawn from the study, but have undergone the phase 1 operation before or on September 15, 2019.

The conditional power (CP) is the probability that the final result will be significant, given the data observed as of the interim analysis. The equation for calculating the CP is as follows:

$$P_{lk}(\theta) = \Phi \left(\frac{-Z_k \sqrt{I_k} - z_{1-\alpha} \sqrt{I_k} - \theta(I_K - I_k)}{\sqrt{I_K - I_k}} \right)$$

Where,

$Z_k = \frac{p_{2k} - p_{1k}}{\sqrt{\sigma^2 \left(\frac{1}{n_{1k}} + \frac{1}{n_{2k}} \right)}}$; p_{2k} and p_{1k} are the adhesion rates of the experimental group and control group at the time of the interim analysis, while n_{2k} and n_{1k} are the numbers of subjects with evaluable primary endpoint in the experimental group and control group at the time of the interim analysis.

$$I_k = \frac{1}{\sigma^2} \left(\frac{1}{n_{1k}} + \frac{1}{n_{2k}} \right)^{-1}$$

$I_K = \frac{1}{\sigma^2} \left(\frac{1}{n_1} + \frac{1}{n_2} \right)^{-1}$, n is the total number of subjects in the experimental group and control group, and in this study, $n_1 = n_2 = 77$;

$\sigma^2 = \bar{p}(1 - \bar{p})$, $\bar{p} = (P_1 + P_2)/2$, P_2 and P_1 are the expected adhesion rates of the experimental group and control group, and in this study, $P_2 = 0.5$, $P_1 = 0.75$;

$$\Theta = P_2 - P_1;$$

$$Z_{1-\alpha} = Z_{1-0.025} = 1.96 \text{ (one-sided 97.5% critical Z-value);}$$

Φ : Area under the standard normal distribution curve

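### The primary proportion has two conflicting denominators, all randomised and evaluable only; the choice costs power and, at low adhesion rates or with unequal missingness, can reverse the verdict

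*Protocol*

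**What the plan says.** Two sets of instructions coexist.

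**All randomised.** Protocol 8.1 has the proportion "calculated as the number of subjects free of adhesions divided by the total number of subjects randomized to that treatment". SAP 3.3.1 has the "number of subjects free of adhesions divided by the total number of subjects randomized to receive the treatment". Both documents make ITT primary and define it as everyone randomised (Protocol 8.9, SAP 2.2).

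**Available or evaluable subjects.**
- Protocol 8.7: "All study endpoints will be analyzed using the available data. There will be no missing data imputation in this study".
- SAP 2.3.5, on the primary endpoint specifically: "no imputation will be made for missing data during primary analyses". Multiple imputation is kept for a sensitivity analysis.
- Protocol 8.2.1 and SAP 1.3.3 need 77 subjects per arm and enrol 110 to allow for 30% dropout. Protocol 8.6 expects that "a total of 154 participants (77 per arm) with evaluable primary endpoint are available by the study completion".
- The interim formula in SAP section 4 uses "the numbers of subjects with evaluable primary endpoint in the experimental group and control group at the time of the interim analysis".

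SAP 2.1 gives a general rule that "the number of subjects without missing data in the analysis set selected will be used as the denominator for percent calculation", but only where nothing else is specified. The code in SAP 3.3.1 is a group-by-outcome table, "tables group*outcome / riskdiff(CL=WALD", run on weighted counts; it does not show how a missing outcome enters those counts.

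**The concern.** Dividing by all randomised while counting only observed adhesion-free subjects in the numerator silently codes each missing assessment as not adhesion-free. That is a single imputation, and it conflicts with the no-imputation rules. No section of either document says how a randomised subject without an assessment is to be classified.

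With 30% dropout expected, this is not a detail. Two programmers could each follow the written plan and reach different conclusions from the same data. The all-randomised version also makes the test partly a comparison of missingness between arms: too liberal if Control has more missing assessments, very conservative if INTERCEED has more. A choice of denominator made after results are visible would be data-driven.

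**Working it through.** **Inputs from the documents.** Adhesion rates 0.50 (INTERCEED) and 0.75 (Control), so adhesion-free 0.50 v 0.25; one-sided alpha 0.025; power 90%; dropout 30%; 110 randomised per arm. Success means the lower Wald limit of INTERCEED minus Control in the adhesion-free proportion exceeds 0.

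**1. The plan's sample size reproduces.** With pooled rate 0.625 and no continuity correction,

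n = [1.960·√(2·0.625·0.375) + 1.2816·√(0.50·0.50 + 0.25·0.75)]² / 0.25² = 76.7, rounded up to 77; and 77/0.70 = 110.

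The 77 are evaluable subjects, so the sample size assumes the available-data denominator.

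**2. Power at the planning rates.** Exact binomial enumeration of the Wald rule. Over all randomised with 30% missing, the adhesion-free proportions become 0.50 × 0.70 = 0.35 and 0.25 × 0.70 = 0.175, so the difference shrinks from 0.25 to 0.175.

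| Denominator | Power |
|---|---|
| 77 evaluable per arm | 90.9% |
| Evaluable number varying around 30% missing | 90.5% |
| All 110, exactly 77 evaluable | 87.3% |
| All 110, missingness varying around 30% | 85.2% |

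The all-randomised rule would need 128 per arm for 90% (power 90.1%).

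**3. Power at low adhesion rates.** Protocol 8.6 reports that investigators saw very few adhesions but gives no figure. I assume 5% v 20%. Over 77 evaluable per arm, power is 83.8%. Over 110, with 0.95 × 0.70 = 0.665 v 0.80 × 0.70 = 0.56, it is 36.1%. If exactly 77 are evaluable in each arm, the latter is 23.9%.

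**4. A reversal.** Assume 77 of 110 evaluable per arm, with 4 v 15 adhesions, so 73 v 62 adhesion-free. The limit is d ± 1.96·√[p₁(1−p₁)/n₁ + p₂(1−p₂)/n₂].

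- Evaluable: 73/77 − 62/77 = 0.143, SE 0.0517, interval 0.041 to 0.244. Success.
- All randomised: 73/110 − 62/110 = 0.100, SE 0.0653, interval −0.028 to 0.228. Failure.

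With 77 evaluable per arm, the exact probability that the two verdicts differ is 3.6% at the planning rates, 45% at adhesion-free 0.90 v 0.75, and about 60% at 0.95 v 0.80.

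**5. Type I error of the all-randomised rule.** No treatment effect, nominal one-sided 2.5%. The documents give only 30% dropout overall; the splits and adhesion rates are my assumptions.

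| Missing, INTERCEED v Control | Adhesions 10% | 20% | 50% |
|---|---|---|---|
| 25% v 35% | 28.8% | 22.0% | 12.3% |
| 28% v 32% | 8.2% | 6.8% | 5.2% |
| 30% v 30% | 2.6% | 2.5% | 2.7% |
| 32% v 28% | 0.6% | 0.7% | 1.2% |
| 35% v 25% | 0.04% | 0.08% | 0.33% |

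The evaluable-subject rule stays at 2.4% to 3.0% under the four unequal splits, provided missingness is unrelated to adhesions.

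**The case against.** The documents lean towards available data. Protocol 8.7 covers every endpoint, and SAP 2.3.5 names the primary one. Planned multiple imputation has little purpose if missing already counts as failure. The sample size and interim rule count evaluable subjects. The mention of all randomised subjects could be read as naming the ITT arm. Run on subjects with outcomes left missing, the printed code would drop them. This shows which reading was probably intended, but does not remove the conflict: SAP 3.3.1 is the specific text and states its denominator outright, SAP 2.1 yields to a specific rule, and the code starts from counts already aggregated.

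The size depends on assumptions. At the planning rates with equal dropout the expected result, about 38 v 19 adhesion-free of 77, succeeds under both rules (lower limits +0.099 and +0.059). Reversal becomes likely only with low adhesion rates or unequal missingness, and with equal missingness type I error is close to nominal. That qualification stands. The loss of power at the planning rates needs no assumption beyond the plan's own 30%.

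The evaluable analysis has its own weakness. Under Protocol 7.1.5, withdrawal can follow an operation for obstructive ileus without image data, so missing assessments may be related to adhesions. In the 4 v 15 example, counting three missing INTERCEED cases as not adhesion-free (73/80 v 62/77) moves the lower limit to −0.001. With equal numbers added to both arms it stays above 0 through 11 per arm and falls to −0.001 at 12. This is a reason for a sensitivity analysis, not for leaving the denominator undefined.

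**Conclusion.** The concern holds. The primary estimate is not uniquely defined, and the denominator as written does not deliver the stated 90% power: it gives 85.2% at the planning rates with 30% missing in each arm (87.3% if exactly 77 are evaluable). The sample size itself is correct, and an available-data analysis delivers its power. The larger effects (36.1% power, the reversed verdict, type I error up to 28.8%) rest on assumed low adhesion rates or assumed unequal missingness. The low-rate case is relevant because the protocol itself reports very low adhesion rates. This must be settled before database lock.

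**What to change.** - In Protocol 8.1 and SAP 3.3.1, make the denominator the randomised subjects with an evaluable primary endpoint, analysed as randomised. This agrees with Protocol 8.7, SAP 2.3.5, the sample size and the interim rule. Keep multiple imputation over all randomised subjects as the sensitivity analysis; the ITT definition and the statement in Protocol 7.1.5 that early withdrawals are included in the analysis can then stand.
- Report the number of missing assessments and their reasons by arm. List separately those possibly related to adhesions (operation for obstructive ileus without image data, adhesion-related death), and add one sensitivity analysis counting them as not adhesion-free.
- If the sponsor prefers all randomised, state that missing counts as failure and restate power as about 85%.
- As separate drafting, align Protocol 7.1.2, 8.3, 8.5 and the definition of P_C in 8.1 to the adhesion-free direction with lower limit above 0, as in the SAP. The two directions are exact complements only under available data.

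The cost is wording in both documents, one listing and one sensitivity analysis, with no new data. The price is that the primary analysis becomes an observed-outcome analysis, exposed to adhesion-related missingness as described above.

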## **8.2. Calculation of Sample Size**

### **8.2.1. Total Sample Size: 220 patients.**

The relevant literature review revealed observed percentages of subjects with pelvic wall adhesions of 41% and 49.3% for INTERCEED™ and of 76% for Control[12,13]. As a consequence, for the sample size determination, the assumption was conservatively made that the proportions of subjects with adhesions in INTERCEED™ and Control groups would be 0.5 and 0.75, respectively. With a one-sided significance level of 0.025, a sample size of 77 subjects in INTERCEED™ group and 77 subjects in Control group are required to achieve 90% power to detect a difference of 0.25 between the two group proportions using a one-sided Chi-square test. In order to adjust for a 30% dropout rate, a total of 110 subjects in INTERCEED™ group and 110 subjects in Control group, for a total of 220 subjects, will be enrolled.

### **8.2.2. Minimum and Maximum Number of Subjects in Each Clinical Trial Institution and Reasons for determination**

A total of 220 Chinese patients undergoing rectal cancer surgery and needing second stage reposition of preventive terminal ileostomy will be enrolled in 12 study sites in China.

## **8.3. Significance Level and Power of Clinical Trial**

The power of the statistical test at which the sample size for the primary effectiveness endpoint was calculated is 90%, and the significance level of the test was set to 0.025 (one-sided).

Within-treatment group two-sided 95% confidence intervals for the proportions of subjects with adhesions will be provided using Clopper-Pearson method. In addition, a one-sided Wald 97.5% confidence interval for the difference in two independent proportions (INTERCEED™ minus Control) will be constructed and used for testing the null hypothesis of superiority stated in section 8.1. If the upper limit of the confidence interval is smaller than 0, then it will be concluded that INTERCEED™ is superior to Control.

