1.3.3 Sample Size

The relevant literature review revealed observed percentages of subjects with pelvic wall adhesions of 41% and 49.3% for INTERCEED™ and of 76% for Control [1,2]. Therefore, for the sample size determination, the assumption was conservatively made that the proportions of subjects with adhesions in INTERCEED™ and Control groups would be 0.5 and 0.75, respectively. With a one-sided significance level of 0.025, a sample size of 77 subjects in INTERCEED™ group and 77 subjects in Control group were required to achieve 90% power to detect a difference of 0.25 between the two group proportions using a one-sided Chi-square test. In order to adjust for a 30% dropout rate, a total of 110 subjects in INTERCEED™ group and 110 subjects in Control group, for a total of 220 subjects, were enrolled.

2 Basic Principles for Statistical Analysis

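### The mandatory stop at conditional power ≤ 60% lowers power from 90% to about 87% under the plan's own assumptions, but both documents still give only the 90%

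*Protocol*

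**What the plan says.** Protocol 8.2.1 assumes that "the proportions of subjects with adhesions in INTERCEED™ and Control groups would be 0.5 and 0.75, respectively". It continues: "With a one-sided significance level of 0.025, a sample size of 77 subjects in INTERCEED™ group and 77 subjects in Control group are required", and these numbers "are required to achieve 90% power to detect a difference of 0.25 between the two group proportions". Protocol 8.3, the section on significance level and power, repeats the figure: "The power of the statistical test at which the sample size for the primary effectiveness endpoint was calculated is 90" percent. SAP 1.3.3 says the same group sizes "were required to achieve 90% power to detect a difference of 0.25 between the two group proportions using a one-sided Chi-square test". The final decision rests on "a one-sided Wald 97.5% confidence interval for the difference in two independent proportions" (Protocol 8.3).

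Protocol 8.6 and SAP section 4, added with version 5.0, introduce an interim analysis once at least 94 subjects (61% of 154) are evaluable. The data are analysed "to determine if the interim results meet the pre-specified threshold of early discontinuation", which is CP ≤ 60%. Both documents word the consequence as mandatory: the study ends if the threshold is met and otherwise runs to completion as planned. The target stays at 154 evaluable and 220 enrolled. Neither document gives the power with this rule in place, gives the chance of stopping when the assumed effect is real, or describes the rule as advisory.

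**The concern.** The 90% belongs to a design with no interim look. Once a trial must stop for futility, every stopped trial counts as a failure, including those that would have ended significant, so power can only fall.

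The fall is not negligible here because of how CP is defined. SAP section 4 computes it under the design effect (θ = P₂ − P₁ = −0.25). A trial stopped at CP just below 60% therefore still has nearly a 60% chance of success if the sponsor's assumption is right.

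Anyone approving version 5.0 needs the resulting power to judge the rule. They would look in Protocol 8.3 and find only the fixed-design figure.

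**Working it through.** **Inputs.** Adhesion rates 0.50 and 0.75, one-sided α = 0.025, 77 evaluable per arm (Protocol 8.2.1). Final Wald rule (Protocol 8.3, 8.5). Look at 94 or more evaluable, stop if CP ≤ 0.60, and a CP table covering looks at 94, 102, 108, 112 and 116 (Protocol 8.6, SAP section 4). σ² = 0.625 × 0.375 = 0.2344 and θ = −0.25 (SAP section 4). Assumed: equal arms at the look and exactly 77 per arm at the end.

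**1. Reproduce the 90%.**
n = [1.96·√(2 × 0.2344) + 1.2816·√(0.25 + 0.1875)]² / 0.25² = (1.342 + 0.848)² / 0.0625 = 76.7, so 77 per arm. Power at 77 on this formula is 90.1%. Exact binomial power is 90.9% (Wald) and 90.6% (pooled chi-square). Allowing for dropout, 77/0.7 = 110 per arm. The stated figures hold for the fixed design.

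**2. Reproduce the CP table.**
CP = Φ{[−Z_k√I_k − 1.96√I_K − θ(I_K − I_k)] / √(I_K − I_k)}.
At 94 subjects (47 per arm), I_k = 47/(2 × 0.2344) = 100.27 and I_K = 77/(2 × 0.2344) = 164.27. For an observed difference of −0.11, Z_k√I_k = −0.11 × 100.27 = −11.03. Then CP = Φ[(11.03 − 25.12 + 16.00)/8.00] = Φ(0.239) = 0.59, as tabulated. This form reproduces every cell to rounding.

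**3. Locate the stopping boundary.**
Setting CP = 0.60 at 94 subjects: d = −(0.2533 × 8.00 + 25.12 − 16.00)/100.27 = −0.111. An observed reduction of 0.111 or less stops the trial.

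**4. Power with the stop, on the plan's sizing formula.**
Success now requires passing the look and winning at the end. These are two correlated normal events with correlation √(47/77) = 0.781.
- Pass the look: standard error √(0.4375/47) = 0.0965; (0.25 − 0.111)/0.0965 = 1.44; probability of stopping 7.5%.
- Win at the end: critical difference 1.96·√(2 × 0.2344/77) = 0.153; standard error √(0.4375/77) = 0.0754; (0.25 − 0.153)/0.0754 = 1.29; probability 90.1%.
- Both: 87.1%. Across all five looks the result is 87.0–87.1%.

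**5. Exact check.**
All interim binomial outcomes under 0.50 and 0.75 were enumerated, those with CP ≤ 0.60 were removed, the rest were combined with the remaining subjects, and the final test was applied.

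| Evaluable at look | Boundary (difference) | Chance of stopping | Power with stop, Wald | Power with stop, chi-square | Stopped trials that would have ended significant |
|---|---|---|---|---|---|
| 94 | −0.111 | 8.5% | 87.1% | 86.9% | 45% |
| 102 | −0.121 | 9.4% | 86.8% | 86.6% | 44% |
| 108 | −0.127 | 7.6% | 88.2% | 88.0% | 36% |
| 112 | −0.131 | 9.5% | 87.2% | 87.0% | 40% |
| 116 | −0.134 | 8.3% | 88.1% | 87.9% | 34% |

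The last column is lost power divided by the chance of stopping. At 94 subjects, (90.92 − 87.10)/8.49 = 45%.

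**6. Sensitivity to method.**
A normal approximation using the planning variance throughout goes from 89.3% to 86.0–86.1%. An unpooled Wald approximation goes from about 91.3% to 87.8–88.0%. Looks at 120 to 150 subjects give about 87–89%. For looks at 94 to 116, the loss against the matching fixed design is 2.6 to 4.1 points in the exact results and 3.0 to 3.5 points in the normal approximations.

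**The case against.** **The sizing sentence is true.** Protocol 8.3 reports the power at which the sample size was calculated, and that figure reproduces. This stands: nothing was miscalculated, and the defect is an omission. But 90% is the only power given for the amended design, in the section a reader would consult.

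**The loss is small and could be a product of mixed methods.** The 86% end does come from the planning-variance approximation, whose own fixed-design power is 89.3%. Comparing like with like, the sizing formula goes from 90.1% to about 87%. The loss is modest but larger than rounding.

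**The SAP formula may be different.** As read from the PDF, SAP section 4 has √I_k, not √I_K, in the critical-value term. Taken literally, exact Wald power with the stop would be 90.5, 90.4, 90.3, 90.0 and 89.5% for looks at 94 to 116, which removes most of the loss. That form does not reproduce the table: at 94 subjects and −0.11 it gives Φ[(11.03 − 19.63 + 16.00)/8.00] = 0.82, against 0.59 in both documents. The subscript may be a reading error, so the table governs here.

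**The rule might be overridden, or the numbers might differ.** If the stop were discretionary, the loss would be smaller, but the text does not say that it is. The look is also tied to a calendar date, so its size is not fixed; the results vary little over the tabulated range.

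**The sponsor already doubted 0.75 versus 0.50.** That is why the look was added. It remains the scenario under which CP is computed and power is claimed, so the power should be right for it.

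**Conclusion.** The point holds. With the stop obeyed, power under 0.75 versus 0.50 is about 87% (86–88% across methods and interim sizes of 94 to 116), not 90%. If the device works as assumed, the trial fails about 12–14% of the time, not 10%. It is stopped in 7.6–9.5% of cases (exact), and a third or more of those would have ended significant.

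This assumes that the rule is applied as written, that CP is in the form matching the published table, that the arms are equal at the look, and that 77 per arm are evaluable at the end. One-sided type I error is not increased, because the look can stop only for futility. The omission should be corrected but does not undermine the design.

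**What to change.** In Protocol 8.2.1 and 8.3 and SAP 1.3.3, replace the bare 90% with wording such as:

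> Under adhesion rates of 0.75 and 0.50 with 77 evaluable subjects per arm, power is 90% for the fixed design and about 87% (86–88%, depending on the size of the interim look and the method of calculation) when the CP ≤ 60% stop is applied. The one-sided type I error is not increased, because the interim look can stop for futility only.

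Protocol 8.6 and SAP section 4 should refer to that statement and add the chance of stopping when the 0.25 effect is real (about 8–10%). The SAP should also confirm that the critical-value term uses the final information I_K, as the table requires.

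The cost is a sentence in each place and a slightly less favourable stated power. No patients are added, and the stopping rule and final test do not change. For scale only: on the sizing formula with a look at 61%, 83 evaluable per arm gives 89.9% and 84 gives 90.3%.
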